4.2 Treatment period

Visit 2 (Baseline Week 0)

- Administer study drug
- Inclusion/Exclusion
- Randomization
- Concomitant medications/procedures
- GI symptoms and pain interference
- PROs (EESAI, EoE-QOL-A, SODA, PedsQL, PEESS, PROMIS)
- Vital Signs, Weight
- Diet Questionnaire
- Adverse Events
- Pregnancy Testing: urine
- Research samples (whole blood/serum/plasma)

Visit 3 (Week 4)

- Administer study drug
- Concomitant medications/procedures
- GI symptoms and pain interference
- PROs (EESAI, EoE-QOL-A, SODA, PedsQL, PEESS, PROMIS)
- Vital Signs, Weight
- Adverse Events
- Pregnancy Testing: urine
- Clinical labs (hematology and serum chemistry, urinalysis)
- Research samples (whole blood/serum/plasma)

Visit 4 (week 8)†

- Administer study drug
- Concomitant medications/procedures
- GI symptoms and pain interference
- PROs (EESAI, EoE-QOL-A, SODA, PedsQL, PEESS, PROMIS)
- Vital signs, weight
- Adverse Events
- Pregnancy Testing: urine
- Research samples (whole blood/serum/plasma)

[†] This visit may be repeated until an EGD can be performed for participants whose EGDs are postponed due to COVID-19. Participants may have study drug administered by their local providers due to COVID-19 travel restrictions and travel risks. In these cases, adverse events and concomitant meds will be assessed by study team via telephone/telemedicine prior to the visit to local provider. Pregancy testing and vitals will occur by local provider or local lab per PI discretion. Results from testing will be provided to the study staff directly from the local provider (via medical record release when necessary). Date and time of study drug injection and post injection monitoring results will also be provided to study staff from the local provider.

Visit 5 (Week 12 - End of Treatment/Early Withdrawal)

- Concomitant medications/procedures
- GI symptoms and pain interference
- PROs (EESAI, EoE-QOL-A, SODA, PedsQL, PEESS, PROMIS)
- Physical Exam, Vital Signs, Weight
- Diet Questionnaire
- Adverse Events

- Pregnancy Testing: urine
- Endoscopy with biopsies
- Endoscopic and Histologic metrics (EREFS, HSS, Lanza score, EG Biopsy Evaluation Form, ED Biopsy Evaluation Form)
- Clinical labs (hematology and serum chemistry, urinalysis, pregnancy testing, IgE)
- Research samples (whole blood/serum, plasma, stool microbiome)

4.3 Follow-up period

Visit 6 (Week 16 Follow-Up)

- Physical Exam, Vital Signs, weight
- Adverse Events
- Pregnancy testing: urine
- Clinical labs (hematology and serum chemistry, urinalysis, IgE)

4.4 Open Label Extension I (OLE I)

Study subjects who complete the 12 week treatment phase (whether on drug or placebo) will be allowed into an extension study, where 3 doses of Benralizumab will be administered every four weeks, and 1 more dose will be administered at an 8 week interval. Study drug may be administered at 8 week intervals due to COVID-19 restrictions or PI discretion depending upon symptoms. General laboratory studies and patient reported outcomes will be measured regularly. Endoscopy will be performed four weeks after the last dose of the study drug. The first dose in the OLE phase will be administered at visit 5 of the double treatment phase, for subjects who choose to do so.

Visit 5 (OLE I Week 12, 1st dose)

- Administer study drug
- Concomitant medications/procedures
- GI symptoms and pain interference
- PROs (EESAI, EoE-QOL-A, SODA, PedsQL, PEESS, PROMIS)
- Adverse Events
- Research samples (whole blood/serum, plasma)

Visit 6 (OLE I Week 16, 2nd dose)

- Administer study drug
- Concomitant medications/procedures
- GI symptoms and pain interference
- PROs (EESAI, PEESSv2, PedsQL3.0, EoE-QOL-A, SODA, PROMIS)

- Vital signs
- Clinical labs (CBC with differential, pregnancy testing)
- Adverse Events
- Research samples (whole blood/serum, plasma)

Visit 7 (OLE I Week 20, 3rd dose)

- Administer study drug
- Concomitant medications/procedures
- GI symptoms and pain interference
- PROs (EESAI, PEESSv2, PedsQL3.0, EoE-QOL-A, SODA, PROMIS)
- Adverse Events
- Research samples (whole blood/serum, plasma)
- Clinical labs (CBC with differential, urinalysis, pregnancy testing)

Visit 8 (OLE I Week 24, safety follow up phone call)

- Concomitant medications/procedures
- GI symptoms and pain interference
- PROs (EESAI, PEESSv2, PedsQL3.0, EoE-QOL-A, SODA, PROMIS)
- Adverse Events

Visit 9[†][†] (OLE I Week 28 – 4th dose)

- Administer study drug
- Concomitant medications/procedures
- GI symptoms and pain interference
- PROs (EESAI, PEESSv2, PedsQL3.0, EoE-QOL-A, SODA, PROMIS)
- Adverse Events
- Research samples (whole blood/serum, plasma)
- Clinical labs (CBC with differential, urinalysis, pregnancy testing)

†† This visit may be repeated until an EGD can be performed for participants whose EGDs are postponed due to COVID-19

At visits 6, 7, and 9 participants may have study drug administered by their local providers due to COVID-19 travel restrictions and travel risks. In these cases, adverse events and concomitant meds will be assessed by study team via telephone/telemedicine prior to the visit to local provider. Pregancy testing, vitals, urinalysis, and CBC with differential will occur by local provider/lab per PI discretion. Results from testing will be provided to the study staff directly from the local provider (via medical record release if necessary). Date and time of
drug injection and post injection monitoring results will also be provided to study staff from the local provider.

Visit 10 (OLE I Week 32, safety follow up phone call)

- Concomitant medications/procedures
- PROs (EESAI, PEESSv2, PedsQL3.0, EoE-QOL-A, SODA, PedsQL, PEESS)
- GI symptoms and pain interference
- Adverse Events

Visit 11 (OLE I Week 36 - End of treatment EGD or Early Withdrawal)

- Concomitant medications/procedures
- GI symptoms and pain interference
- PROs (EESAI, PEESSv2, PedsQL3.0, EoE-QOL-A, SODA, PROMIS)
- Adverse Events
- Endoscopy with biopsies
- Endoscopic and Histologic metrics (EREFS, HSS, Lanza score, EG Biopsy Evaluation Form, ED Biopsy Evaluation Form)
- Clinical labs (CBC with differential, urinalysis, pregnancy testing)
- Research samples (whole blood/serum)

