*= Procedures in Visit 5/6 (F/U) which will only be performed if subject does NOT continue to OLE 1

**= Procedures in Visit 5/6 (F/U) which will only be performed if subject is to start OLE 1.

***= drug administration in visit 11 will only be performed if subject chooses to continue to OLE2.

* visit window is counted from the previous visit and not from the date of enrollment/randomization.

⁺ This visit may be repeated until an EGD can be performed for participants whose EGDs are postponed due to COVID-19.

+ + This visit may be repeated until an EGD can be performed for participants whose EGDs are postponed due to COVID-19

Note: study drug administration may occur at local provider per PI discretion at visits 4, 6, 7, and 9 due to COVID-19

Study Procedures	OLE II													
	V12 OLE II	V13 OLE II	V14 OLE II	V15 OLE II	V16 OLE II	V17 OLE II	V18 OLE II	V19 OLE II	V20 OLE II	V21 OLE II	V22 OLE II	V23++ OLE II	V24 EOT/EW EGD	V25 Safety F/U
Week (Wk)	40	44	48	52	56	60	64	68	72	76	80	84	88 or 92	96
Visit window in days (d) *	±4 d	±4 d	±4 d	±4 d	±4 d	±4 d	±4 d	±4 d	±4 d	±4 d	±4 d	±4 d	±4 d	±4 d
Diet Questionnaire			х			х							х	х
Administer study drug ¹	X1	х	X1	х	X1	х	X1	х	X1	х	X1	х		
Con meds/procedures	х	х	х	х	х	х	х	х	x	х	х	х	х	х
Efficacy:														
EESAI ²						х							х	
EoE-QOL-A ³						х							х	
GI symptoms and pain interference						х							Х	Х
SODA ⁴						х							х	
EREFS⁵													х	
PEESSv2 ⁶						х							х	
PedsQL 3.0 ⁷						х							х	
PROMIS ⁸						х							х	
Lanza Score													х	
Histology Assessments ⁹													х	
Safety:														
Weight		х		х		х		х		х		х	х	
Vital signs	X*	х	Х*	х	Х*	х	X*	х	X*	х	Х*	х	х	
Physical Exam						х							х	
Adverse events	X*	х	Х*	х	Х*	х	X*	х	X*	х	X*	х	х	
Lab testing:														
Hematology and serum chemistry													х	
CBC with Differential		х		х		х		х		х		х	х	

Study Procedures		OLE II													
	V12 OLE II	V13 OLE II	V14 OLE II	V15 OLE II	V16 OLE II	V17 OLE II	V18 OLE II	V19 OLE II	V20 OLE II	V21 OLE II	V22 OLE II	V23†† OLE II	V24 EOT/EW EGD	V25 Safety F/U	
Week (Wk)	40	44	48	52	56	60	64	68	72	76	80	84	88 or 92	96	
Visit window in days (d) ⁺	±4 d	±4 d	±4 d	±4 d	±4 d	±4 d	±4 d	±4 d	±4 d	±4 d	±4 d	±4 d	±4 d	±4 d	
IgE						х							х		
Urinalysis													x		
Pregnancy testing – Urine	X*	х	X*	х	Х*	х	X*	х	Х*	х	X*	х	х		
Endoscopy with biopsies ¹⁰													х		
Research samples (whole blood/serum)	X*	x	X*	х	X*	х	X*	х	X*	х	X*	x	x		

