4.5 Extended Open Label Extension (OLE II)

Study subjects may choose to extend the OLE period, and receive up to 7 additional injections of benralizumab (every8 weeks) or 13 additional injections (every 4 weeks dosing), based on clinical considerations by the treating physician. The default dosing will be every 8 weeks. A research endoscopy will occur in visit 24 (end of treatment). Any other endoscopies will be performed clinically as needed, per the discretion of the PI. Medications will be modified ad lib during the OLE II period.

Visit 11 (Week 36) through Visit 25 (Week 92)

During OLE II, study drug will be administered at either 4 or 8 week intervals, which will be determined ad-lib by the study doctor, depending upon the symptoms, CBC results and discussion with patients. Additional unscheduled clinical tests such as CBC with differential tests (for peripheral eosinophil counts) may be drawn to determine dosing frequency and assess patient wellbeing. If the study drug is given at 8 week interval, then telephone encounter and surveys will be completed remotely every four weeks. For participants whose EGDs are postponed due to COVID-19, additional injections may be given until an EGD can be performed.

The below activities are done when indicated in the study plan table (section 4):

- Concomitant medications/procedures
- GI symptoms and pain interference
- PROs (EESAI, EoE-QOL-A, SODA, PedsQL, PEESS, PROMIS)
- Vital Signs, Weight
- Adverse Events
- Pregnancy Testing: urine
- Endoscopy with biopsies
- Endoscopic and Histologic metrics (EREFS, HSS, Lanza score, EG Biopsy Evaluation Form, ED Biopsy Evaluation Form)
- Physical exam (Due to COVID-19, physical exams not associated with EGDs may be conducted via telephone or telemedicine)
- Clinical labs (hematology and serum chemistry, urinalysis, pregnancy testing, IgE)
- Research samples (whole blood/serum, plasma, stool microbiome)

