9.3 Study timetable and end of study

The end of study will be at a follow up visit at Week 16 ± 3 days. For subjects who are remote, the follow up visit can be performed at a local site, in which vital signs, physical exam, urine pregnancy and lab work will be performed. Results will be released to CCHMC upon authorization of release of medical information/specimen by the subject.

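### A subject who completes OLE I and declines OLE II has no scheduled safety contact after the Week 36 biopsy endoscopy

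*Combined protocol and SAP*

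**What the plan says.** - **OLE I ends at V11.** The last visit in Section 4.4 is "Visit 11 (OLE I Week 36 - End of treatment EGD or Early Withdrawal". It includes biopsies and an adverse-event (AE) review. The first part of the Section 4 study plan table also stops at V11, Week 36.
- **OLE II is optional.** Section 4.5 opens with "Study subjects may choose to extend the OLE period", and a table footnote says that "drug administration in visit 11 will only be performed if subject chooses to continue to OLE2". V12 to V25 appear only under OLE II; the 4.5 visit heading reads "Visit 11 (Week 36) through Visit 25 (Week 92)".
- **A V5 leaver has a follow-up.** Section 4.3 provides "Visit 6 (Week 16 Follow-Up)" with an examination, vital signs, AEs, a pregnancy test and laboratory work. A table footnote marks "Procedures in Visit 5/6 (F/U) which will only be performed if subject does NOT continue to OLE 1". V11 has no equivalent footnote for those who do not continue.
- **End of study.** Section 9.3 states "The end of study will be at a follow up visit at Week 16" and names no later end-of-study visit.
- **AE and SAE periods.** Section 6.4.1 collects AEs until the subject completes participation, or for 30 days after premature withdrawal. Section 6.4.2 follows AEs already known to be unresolved. Section 6.5 sets serious adverse event (SAE) reporting to 60 days after the last dose.
- **Section 3.3** refers to a 30-day safety follow-up after which participation ends. The sentence that would define its scope is damaged.

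**The concern.** Finishing OLE I and stopping is a permitted exit, and its last act is an EGD with biopsies. Section 1.2.2 names bleeding, perforation and transient bacteremia among the risks of that procedure. V11 can record what is evident on the day, but nothing is scheduled to ask about events that appear after the subject goes home.

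The other two planned exits each have a later contact. If the Section 3.3 follow-up does not reach this group, there is also an oddity in Section 6.4.1: a subject who completes OLE I has AE collection closed on the day of the biopsies, while one who withdraws prematurely has 30 further days.

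At stake is the completeness of post-procedural safety data in the extension, not any efficacy conclusion.

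**Working it through.** **Inputs.** From the Section 4 table: V4 Week 8, V5 Week 12, V6 Week 16, V9 (last OLE I dose) Week 28, V11 Week 36, V23 (last OLE II dose) Week 84, V24 Week 88 or 92, V25 Week 96. The visit window is ±4 days, counted from the previous visit. The 4.5 heading puts V25 at Week 92 instead. On EGD timing, Section 4.4 says "Endoscopy will be performed four weeks after the last dose of the study drug", whereas the table places V11 eight weeks after V9. Both timings are carried through.

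**Step 1: scheduled contact after the last EGD.**
- V5 leaver: (16 − 12) × 7 = 28 days. This is the plan's own interval.
- OLE I leaver: none.
- OLE II leaver, V25 at Week 96: (96 − 92) × 7 = 28 days or (96 − 88) × 7 = 56 days. With V25 at Week 92: 0 or 28 days. The zero would put the follow-up on the day of a Week 92 EGD, which is hardly intended.

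**Step 2: last scheduled contact after the last dose.**
- V5 leaver: (16 − 8) × 7 = 56 days.
- OLE I leaver: (36 − 28) × 7 = 56 days on the table weeks; 28 days on the 4.4 wording.
- OLE II leaver: (96 − 84) × 7 = 84 days, or (92 − 84) × 7 = 56 days.

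On the table weeks the V5 and OLE I exits match, so what differs is the time after the procedure.

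**Step 3: part of the 60-day SAE period left after V11.**
- Table weeks: 60 − 56 = 4 days. Two ±4-day steps (V9 to V10, V10 to V11) put V11 on day 48 to 64, leaving 0 to 12 days.
- 4.4 wording: 60 − 28 = 32 days. One ±4-day window puts the EGD on day 24 to 32, leaving 28 to 36 days.

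**Step 4: does another section supply a contact?**
- 9.3: no. Its visit is 36 − 16 = 20 weeks before V11.
- 6.4.2: no. It follows known events and does not look for new ones.
- 6.5: no. It sets a reporting period without a contact.
- 6.4.1 and 3.3: this depends on the scope of the 30-day follow-up. If it covers every exit, AE collection stays open after V11 but no visit or call is listed. If it covers OLE II only, collection closes at V11.

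**Step 5: when a call should fall.** Thirty days after the EGD is day 56 + 30 = 86 after the last dose on the table weeks, well past day 60. On the 4.4 wording it is day 28 + 30 = 58, two days short. For the earliest EGD on that timing (day 24), the call must be on day 60 − 24 = 36 after the EGD. A call on day 32 would reach only day 24 + 32 = 56.

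**The case against.** The strongest reply is Section 3.3. The 30-day follow-up closes a summary of all study phases, and nothing legible limits it to OLE II. If it is general, this group does have a follow-up and lacks only a visit number. The study flow chart is also not available in the text, so a note there cannot be excluded. This stands as far as it goes: no contradiction with 3.3 can be claimed. It does not supply the missing contact in the table or in 4.4.

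A reader might infer that delayed events in this group could reach the study only through unsolicited reports. The documents do not support that. Section 3.3 may keep follow-up open, and 6.4.1 lists interviewing the participant as a way of finding AEs without tying it to numbered visits.

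The comparators have limits. V6 is a general follow-up and is not described as a post-endoscopy check. After the last dose an OLE I leaver has two contacts (the V10 safety call and V11), as does a V5 leaver (V5 and V6). The V25 cell of the AE row is blank in the extracted table, although concomitant medications are marked. This confines the point to the time after the procedure.

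Finally, Section 1.2.2 says few patients have unexpected or serious complications and gives no timing for them, so the documents do not establish 30 days as the right interval. That is fair. The interval is borrowed from 3.3 and 6.4.1.

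**Conclusion.** The point holds as a minor, inexpensive improvement. Table 1 and Section 4.4 schedule no contact after the V11 EGD for a subject who completes OLE I and declines OLE II, against 28 days for a V5 leaver and, with V25 at its table week, 28 or 56 days for an OLE II leaver.

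This rests on the table and the 4.4 visit list being complete as read. It does not depend on how 3.3 is resolved, because a scheduled contact is missing on either reading.

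The expected yield is low. The number affected is not given: it could be zero and is at most about 26, the planned enrolment. It would be wrong to infer that follow-up after the last dose is generally shorter for this group: on the table weeks it equals that of a V5 leaver, and only the 4.4 wording shortens it to 28 days. The randomised double-blind comparison is unaffected.

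**What to change.** Add a V11 footnote and one line in Section 4.4. A subject who does not enter OLE II has one telephone safety contact in the V8/V10 format, covering AEs and concomitant medications. It takes place about 30 days after the V11 EGD and no earlier than 60 days after the last dose. Participation and AE collection under 6.4.1 end at that contact.

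The second condition matters on the 4.4 four-week timing, where day 36 after the EGD covers the earliest EGD. AE collection should not close at a fixed day 30, which could precede the end of the SAE period. If the 3.3 follow-up was meant for every exit, this gives it a scheduled contact; if not, it adds one.

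The cost is one footnote, one line and one call per OLE I leaver, at most about 26 calls. These subjects stay in the study about 30 to 36 days longer. No procedure or clinic visit is added.

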4.5 Extended Open Label Extension (OLE II)

Study subjects may choose to extend the OLE period, and receive up to 7 additional injections of benralizumab (every8 weeks) or 13 additional injections (every 4 weeks dosing), based on clinical considerations by the treating physician. The default dosing will be every 8 weeks. A research endoscopy will occur in visit 24 (end of treatment). Any other endoscopies will be performed clinically as needed, per the discretion of the PI. Medications will be modified ad lib during the OLE II period.

Visit 11 (Week 36) through Visit 25 (Week 92)

During OLE II, study drug will be administered at either 4 or 8 week intervals, which will be determined ad-lib by the study doctor, depending upon the symptoms, CBC results and discussion with patients. Additional unscheduled clinical tests such as CBC with differential tests (for peripheral eosinophil counts) may be drawn to determine dosing frequency and assess patient wellbeing. If the study drug is given at 8 week interval, then telephone encounter and surveys will be completed remotely every four weeks. For participants whose EGDs are postponed due to COVID-19, additional injections may be given until an EGD can be performed.

The below activities are done when indicated in the study plan table (section 4):

- Concomitant medications/procedures
- GI symptoms and pain interference
- PROs (EESAI, EoE-QOL-A, SODA, PedsQL, PEESS, PROMIS)
- Vital Signs, Weight
- Adverse Events
- Pregnancy Testing: urine
- Endoscopy with biopsies
- Endoscopic and Histologic metrics (EREFS, HSS, Lanza score, EG Biopsy Evaluation Form, ED Biopsy Evaluation Form)
- Physical exam (Due to COVID-19, physical exams not associated with EGDs may be conducted via telephone or telemedicine)
- Clinical labs (hematology and serum chemistry, urinalysis, pregnancy testing, IgE)
- Research samples (whole blood/serum, plasma, stool microbiome)

At visits 12 - 23 participants may have study drug administered by their local providers due to COVID-19 travel restrictions and travel risks. In these cases, adverse events and concomitant medications will be assessed by study team via telephone/telemedicine prior to the visit to local provider. Pregancy testing, vitals, and CBC with differential will occur by local provider/lab per PI discretion. Results from testing will be provided to the study staff directly from the local provider (via medical record release if necessary). Date and time of drug injection and post injection monitoring results will also be provided to study staff from the local provider.

5. STUDY ASSESSMENTS

5.1 Efficacy assessments

Severity of Dyspepsia Assessment (SODA)

Since instruments are not available to date for adult EG, this study will use the Severity of Dyspepsia Assessment (SODA) scale as a validated instrument to assess dyspepsia related health [25].

EREFs

The EREFs measures EoE esophageal mucosal inflammatory and remodeling features as identified during endoscopy. The score includes a total of 17 items related to the presence and

severity of esophageal features. Specific esophageal features assessed include: rings (absent, mild, moderate, severe, not applicable); stricture (yes, no, not applicable); diameter of the stricture (if applicable); exudates (absent, mild, severe), furrows (absent, present); edema, (absent, present); crêpe paper esophagus (absent, present); overall general appearance incorporating all endoscopically identified EoE findings (ie, fixed rings, strictures, whitish exudates, furrowing, edema, and crêpe paper mucosa). Mucosal changes associated with gastroesophageal reflux disease will also be recorded using the Los Angeles classification system for erosions (No Erosions or LA Classification A, B, C, D). The EREFS is a validated scoring system for the assessment of inflammatory and remodeling features of disease using both overall scores and scores for each individual characteristic [26]. The EoE-EREFS should be performed by the physician who performs the endoscopy procedure.

Lanza Score

The Lanza score is an endoscopic grading system used to evaluate for gastritis. It has been used in therapeutic trials and is based on the 0-7 scale with 0=no lesions and 7=>3mm ulcer scale. Since no system has been developed/used to date for EG, this score will be used to assess adult EG [27].

HSS (EoE)

The HSS is a scale developed by Collins, et al. [28] to express the severity and extent of abnormalities in the gastrointestinal (GI) tract that often accompany eosinophilic inflammation. The HSS evaluates esophageal biopsies for various features (e.g. basal layer hyperplasia, dilated intercellular spaces, surface epithelial alteration, apoptotic epithelial cells), eosinophilic inflammation (peak count, eosinophil abscess, eosinophil surface layering), and lamina propria (fibrosis).

Eosinophilic Gastritis (EG) and Eosinophilic Duodenitis (ED) Biopsy Evaluation Forms

Histological evaluation forms, with the goal of capturing features of eosinophilia relevant to the affected tissue as well as other features indicative of mucosal health and inflammation, have been developed by expert pathologist [name]. These forms will be utilized to evaluate the gastric and duodenal biopsies from subjects with extraesophageal eosinophilia.

